The endpoint will be analysed using the same methodology as that described for the primary analysis, except that the test will be based on the number of monthly days with acute medication use during Weeks 1-4.

Change from Baseline in Average Monthly Days with Acute Medication Use (Weeks 1-12)

The endpoint will be analysed using the same methodology as that described for the primary analysis, except that the test will be based on the estimated mean monthly days with acute medication use, which is averaged over Weeks 1 to 4 (Month 1), Weeks 5 to 8 (Month 2), and Weeks 9 to 12 (Month 3). All the medication collected in eDiary as acute medication taken to stop headache/migraine attack will be accounted for in the analysis.

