3.6 Definition of Migraine, Headache Days

For the purpose of endpoint derivations, the following definitions of migraine and headache days will be used:

In this trial, the term headache will encompass both headaches and migraine headaches. Migraine headaches (henceforth simply referred to as “migraines”) are a subgroup of headaches with characteristics outlined below (Section 3.6.1). Using this definition, all migraines are headaches but not all headaches are migraines.

Headaches will be self-reported by the participant using an electronic headache diary on a daily basis from the time of screening until EoT/Withdrawal Visit. The eDiary is split into three parts: the headache diary, the aura without headache diary and the evening diary. The headache diary is the part of the eDiary where the start and stop date and times of experienced headaches are recorded along with headache characteristics and the intake of acute headache/migraine medication. Headache items will be assessed with a yes/no response; severity of pain will be rated as mild, moderate, or severe.

The headache diary is available all day. Participants are required to provide information on headache characteristics including associated symptoms and acute migraine medication intake on each day of an (ongoing) headache (either when a headache has ended or during the evening routine if the headache is ongoing).

The aura without headache diary is the part of the eDiary where data is collected on whether the participant experienced an aura without a headache and whether and what kind of acute headache medications were taken in relation to this event.

The evening diary is the part of the eDiary, that participants are expected to complete each evening. It collects data on acute migraine medication that was taken preventively and triggers the evening routine including the headache and aura without headache diaries.

Panel 3 IHS ICHD-3 Guidelines for Migraine

1.1 Migraine without aura	1.2 Migraine with aura
A. At least five attacks fulfilling criteria B to D	A. At least two attacks fulfilling criteria B and C
B. Headache attacks lasting 4 to 72 hours (when untreated or unsuccessfully treated)	B. One or more of the following fully reversible aura symptoms: 1. visual 2. sensory 3. speech and/or language 4. motor 5. brainstem 6. retinal

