3.9.2 Definition of MOH during the trial

Panel 4 IHS ICHD-3 Guidelines for MOH

- A. Headache occurring on ≥ 15 days/month in a patient with a pre-existing headache disorder
- B. Regular overuse for >3 months of one or more drugs that can be taken for acute and/or symptomatic treatment of headache
- C. Not better accounted for by another ICHD-3 diagnosis

Regular overuse is defined either on:

- 10 days of use/month or more for >3 months of ergotamine, triptan, opioid (butorbital in US), or combination of analgesics
- 15 days of use/month or more for >3 months of non-opioid analgesics (paracetamol [acetaminophen], acetylsalicylic acid, NSAIDs)

In [Panel 4](#) above, the IHS ICHD-3 Guidelines for MOH are stated and used to confirm the MOH diagnosis at the screening visit.

During the trial, to evaluate whether a participant continues to overuse acute migraine medication, the eDiary data will be used for a specific post-baseline 4-week period (28-day period) only and the steps below will be followed:

Check acute migraine medication overuse in the reported month.

Count the number of days on which a medication was taken to treat a headache for each pre-defined acute migraine medication in the reported month (28-days period).

If the participant meets any of the following criteria in the reported month, the participant is considered as overusing acute migraine medication, used as “MOH” in the endpoint definitions. N is the number of monthly days.

- $N \geq 10$ days with either ergotamine, or $N \geq 10$ days with triptan
- $N \geq 10$ days with combination of two or more drug classes among ergotamine, triptan, opioid analgesic and non-opioid analgesics
- $N \geq 10$ days on which combination analgesics are taken.
- $N \geq 15$ days on which a non-opioid analgesic (paracetamol, acetylsalicylic acid, NSAIDs, analginum, antipyrine, tolfenamic acid) is taken. The overuse could be with a single non-opioid analgesic or with several of them.

4 Analysis Sets

The following analysis sets will be used to analyse and present the data:

- *all-participants-screened set (APSS)*
- *all-participants-randomized set (APRS)* – all randomized participants
- *all-participants-treated set (APTS)* – all participants in the APRS who received an infusion of the IMP in the Placebo-controlled Period
- *full-analysis set (FAS)* – all participants in the APTS who had a valid baseline assessment and at least one valid post-baseline 4-week assessment of MMDs in Weeks 1-12

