The week 4 endpoint will be analysed using the same methodology as that described for the primary analysis, except that the test will be based on monthly days with acute migraine medication use. The baseline MMDs will be replaced with monthly acute migraine medication use at baseline. The estimates will be presented with p-values and 95% CIs. For the week 12 endpoint, the estimated mean difference of monthly days with acute migraine medication uses on eptinezumab and placebo will be averaged over Weeks 1 to 4 (Month 1), Weeks 5 to 8 (Month 2), and Weeks 9 to 12 (Month 3). All medication collected in the eDiary as acute migraine medication regardless of whether they are taken to stop headache/migraine attacks will be accounted for in the analysis.

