15.1.4 Migraines/Headaches with Severe Pain Intensity and Migraine Attacks/Headache Episodes

The percentage of migraines/headaches with severe pain intensity is derived based on the derived number of monthly migraine attacks and headache episodes.

Migraine attack and headache episodes are defined in the Section 3.8. Headache severity is collected on a 3-point scale, Mild, Moderate and Severe. Migraines and headaches with severe pain intensity on at least one day are defined as migraine attacks/headache episodes with a reported severity of “Severe”.

The following describes the derivation of number of monthly migraine attacks. The derivation of monthly headache episodes follows the same principles.

The derivation of the number of monthly migraine attacks will follow the imputation rules described in Section 15.1.1 for MMDs, replacing *Reported Migraine Days* with *Reported Migraine Attacks* everywhere. As an example, the number of monthly migraine attacks for a participant with 14 days or more of eDiary reporting in a 4-week period will be derived as:

$$28 * (\text{Reported Migraine Attacks}/\text{Reported eDiary Days})$$

The number of monthly migraines with severe pain intensity is derived in the same way using only migraine attacks with a reported severity of “Severe”.

The percentage of migraines and headaches with severe pain intensity is then calculated as the percentage of migraine attacks/headache episodes with severe pain intensity out of the number of migraine attacks/headache episodes. Participants with no migraine attacks/headache episodes are included with a rate of 0.

15.1.5 Monthly Days with Acute Migraine Medication Usage and MMDs with Acute Migraine Medication Usage

In the aura without headache and headache diaries, as well as the evening diary, participants are asked each day to fill out whether they used any of the following medications during that day: ergotamine, triptan, non-opioid analgesic, barbiturates, opioid, or combination analgesic. A day where the participant answers that they took any of those in the diary is considered a day with use of acute migraine medication.

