The number of days with acute migraine medication usage is then derived for each 4-week period using the imputations described in Section 15.1.1 and replacing *Reported Migraine Days* with *Reported Acute Migraine Medication Days* everywhere as well as replacing *Reported eDiary Days* with *Reported Medication Days*, where a “*Reported Medication Day*” is defined as

a Reported eDiary Day where at least one of the following pieces of information are available:

- A response in the Headache eDiary question “Did you take any medications to treat this headache today?”
- A response in the Evening eDiary question “Did you take any medication to prevent a headache today?”
- A response in the Aura without Headache eDiary question “Did you take any headache medication related to this aura today?”

A missing Medication Day is defined as a day that is not a Reported Medication Day.

If a reported acute migraine medication span across two 4-week periods, then it will be counted in both periods according to the medication start date/preceding period end date and subsequent period start date/medication end date.

The number of days with each available medication type taken will be derived in a similar manner as above.

Additionally, the MMDs with acute migraine medication usage will be derived. The number of MMDs with acute migraine medication is derived in a similar manner as above, except that only days that qualify as a migraine day will be considered.

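### On-trial MOH status counts only days when medication treated a headache, so a participant whose days of use reach the overuse threshold can be scored as not MOH

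*Protocol*

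**What the plan says.** **On-trial MOH status.** SAP 3.9.2 uses Panel 4 to confirm the diagnosis at screening, then sets its own rule for each post-baseline 28-day period. The rule opens: "Count the number of days on which a medication was taken to treat a headache for each pre-defined acute migraine medication". The criteria that follow compare N with 10 days (ergotamine, triptan, combinations of drug classes, combination analgesics) or 15 days (non-opioid analgesics). SAP 15.1.6 sends the CM and MOH endpoints to Section 3.9.

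**Overuse thresholds.** Panel 4 states them as days of use per month of drugs that can serve as acute treatment. It does not ask why the drug was taken on a given day.

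**Medication-day endpoints (Steps 8 and 9).** SAP 11.4.2 brings in "All medication collected in the eDiary as acute migraine medication regardless of whether they are taken to stop headache/migraine attacks". SAP 15.1.5 names the sources: "In the aura without headache and headache diaries, as well as the evening diary, participants are asked each day" about use of the listed drugs. Its questions include "Did you take any medication to prevent a headache today" and "Did you take any headache medication related to this aura today". SAP 3.6 says of the evening diary: "It collects data on acute migraine medication that was taken preventively". SAP 15.1.5 adds that days per medication type are obtained in a similar way.

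**Protocol.** Section 16.8.4, under the Weeks 1-12 medication-day endpoint, says that "acute medication taken to stop headache/migraine attack will be accounted for in the analysis". SAP Section 18 does not mention the SAP's wider wording.

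**The concern.** MOH status is a threshold on a count of days. If preventive intake is left out of the count, a participant can reach the threshold on days of use and still fall below it on the days that are counted. The data needed to see this are collected every day, and the same SAP uses them for another endpoint.

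The MOH-only endpoints (Weeks 1-4 and Weeks 1-12) depend on this count alone, because the on-trial rule has no headache-day condition. The composite of neither CM nor MOH, tested under alpha control at Steps 5 and 6 of SAP 11.2, depends on it jointly with CM. The participants exposed are those close to the cut-off, and they are the ones who decide a responder endpoint.

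**Working it through.** The plan gives no figure for this rule. Its sample size (270 per group) rests on the primary endpoint and is unaffected.

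**1. The counting rules side by side**

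| Rule | Place | Condition on purpose |
|---|---|---|
| Overuse threshold | SAP Panel 4 | none |
| On-trial MOH, opening instruction | SAP 3.9.2 | treating a headache |
| On-trial MOH, listed criteria | SAP 3.9.2 | none stated |
| Medication-day endpoint | SAP 11.4.2, 15.1.5 | none; three diaries |
| Days per medication type | SAP 15.1.5 | none; as the row above |

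**2. When the literal rule changes the status**

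Take one drug class and a complete 28-day diary, so that prorating multiplies by 28/28 = 1. Let T be days with headache treatment, P days with preventive intake only, A days with intake only for aura without headache, and k the threshold.

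- Literal 3.9.2 count: N = T.
- All-use count: N = T + P + A.
- The status differs when T < k ≤ T + P + A.

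Examples:

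- Triptan, T = 8, P = 4, A = 0, k = 10: literal N = 8, below 10, so not MOH. All use is 8 + 4 = 12, at or above 10.
- Non-opioid analgesic, T = 12, P = 4, A = 0, k = 15: literal N = 12, below 15, so not MOH. All use is 12 + 4 = 16, at or above 15.
- Triptan, T = 9, P = 1, A = 0, k = 10: one preventive day is enough, since 9 < 10 ≤ 10.

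**3. How sensitive the status is to preventive or aura-related intake**

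The documents do not say how common such days are. As an assumption, let each of D use days independently be something other than headache treatment with probability q. The literal count X is then Binomial(D, 1 − q), and the chance of falling below the threshold is P(X < k). For D = k = 10 this is 1 − (1 − q)^10; at q = 0.05 it is 1 − 0.95^10 = 0.40.

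| Total use days D, threshold k | q = 5% | 10% | 20% | 30% |
|---|---|---|---|---|
| 10 days, k = 10 | 0.40 | 0.65 | 0.89 | 0.97 |
| 12 days, k = 10 | 0.02 | 0.11 | 0.44 | 0.75 |
| 16 days, k = 15 | 0.19 | 0.49 | 0.86 | 0.97 |

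The range shows that the effect is concentrated near the cut-off. It does not estimate how many participants are affected.

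**4. From status to endpoint**

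- MOH-only, Weeks 1-4: the changed status is the endpoint.
- Step 5: the participant also has to be free of CM, which under SAP 3.9.1 means fewer than 15 headache days or fewer than 8 migraine days.
- Step 6: under SAP 15.1.6, CM and MOH must both be unfulfilled in every available 28-day period. The counting rule matters only if T stays below k in all of them and the all-use count reaches k in at least one.

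**The case against.** **The SAP may already mean the wider count.** The purpose phrase stands only in the opening sentence of 3.9.2. The listed criteria are neutral on purpose, and 15.1.5 derives per-type days from all three diaries. A programmer who used those counts would not misclassify anyone. This stands as far as it shows ambiguity. It does not clear the plan, because 15.1.6 points to Section 3.9, and the instruction there is the narrower one.

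**Panel 4 asks for more than a day count.** It needs more than 3 months of overuse and headache on at least 15 days a month. This stands: 12 triptan days in 28 reach the 10-day threshold but do not establish an ICHD-3 diagnosis. The on-trial rule drops both conditions, which makes MOH easier to fulfil, and Weeks 1-12 requires freedom in all available periods. A reader might infer that the plan understates MOH overall. The documents do not show the net direction against ICHD-3.

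**There are two clearly different counts, not three.** A reader might infer three from the protocol wording. Stopping an attack and treating a headache are close; they part mainly on aura without headache with medication, which SAP 3.8.1 calls a migraine attack. The clear gap is preventive intake. The protocol's endpoint name carries no purpose condition, so the SAP's wider wording can be read as clarification, and its absence from Section 18 is a documentation point.

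**The endpoints do not strictly contradict each other.** A reader might infer that Steps 5-6 and Steps 8-9 conflict. One is a threshold composite and the other a mean change in days; they can differ under any counting rule.

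**Conclusion.** The point holds in a limited form. Followed as written, SAP 3.9.2 can score a participant at or above the 10- or 15-day threshold as not MOH, because preventive intake that the diary records is not counted. The example of 8 + 4 = 12 days against N = 8 follows from the text, assuming a complete diary, a single drug class and preventive intake on separate days. The effect is direct on the MOH-only secondary endpoints and conditional on CM for Steps 5 and 6. The primary endpoint is untouched.

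The number of participants affected is unknown. A reader might infer a bias in favour of eptinezumab, or that patients who move from treating to pre-empting headaches after the brief intervention will be scored as resolved. The second would follow for anyone who did so and crossed the cut-off, but the documents give no frequency of preventive intake. Both arms receive the intervention, and nothing shows a difference between them.

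**What to change.** In SAP 3.9.2, replace the headache-treatment count with the per-class days of use from the headache, aura-without-headache and evening diaries, as derived in 15.1.5 with its Reported Medication Day and prorating rules. State that this count is N in every MOH criterion. The headache-treatment-only count can be kept as a sensitivity analysis. In Section 18, record that 11.4.2 counts acute medication for any purpose, where Protocol 16.8.4 refers to stopping an attack.

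The cost is a few lines of SAP text and a change of input in the derivation; the diary data and per-type counts already exist, and no sample-size figure moves. The downside is that fewer participants may be classed as not MOH in both arms. The change should be settled before the placebo-controlled data are unblinded; if that has already happened, the all-use version should be reported as a labelled sensitivity analysis.

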16.8.5 Sensitivity Analyses of the Key Secondary Endpoints

Sensitivity analyses of the key secondary endpoints will be described in the SAP.

16.8.6 Testing Strategy

For the primary endpoint (change from baseline in MMDs [Weeks 1-4]), test the hypothesis of no difference between the eptinezumab and placebo using a two-sided test on 5% significance level. If rejected and if the test shows a numerical advantage to eptinezumab, then continue to the first key secondary endpoint (change from baseline in MMDs [Weeks 1-12]).

On the first key secondary endpoint, test the hypothesis of no difference between the eptinezumab and placebo groups. If rejected and if the test shows a numerical advantage to eptinezumab, then continue to the second key secondary endpoint (change from baseline in MHDs [Weeks 1-4]). This continues through the list of key secondary endpoints (change from baseline in MHD [Weeks 1-12], not fulfilling the ICHD-3 diagnostic criteria for CM nor MOH [Week 4], not fulfilling the ICHD-3 diagnostic criteria for CM nor MOH [Week 12], change from baseline in average Daily Pain assessment score [Weeks 1-2], change from baseline in monthly days with acute medication use [Weeks 1-4], change from baseline in monthly days with acute medication use [Weeks 1-12]), until an endpoint fails to reach significance.

16.8.7 Analysis of the Secondary Endpoints

The binary secondary endpoints will be analysed using Cochran-Mantel-Haenszel test including previous treatment failures as stratification variables.

All continuous secondary endpoints addressing changes from baseline to Weeks 1 to 4, Weeks 1 to 12, or Weeks 12 to 24 will be analysed using the same methodology as that described for the primary analysis.

50% Response in MMDs (Weeks 1-4): Defined as a 50% reduction in the average MMDs across the available data from Weeks 1 to 4, will compare eptinezumab *versus* placebo. A logistic regression model will be used, with treatment group as a factor, baseline MMDs as a continuous covariate, and previous treatment failures as a binary covariate. Similar analysis will be done for Weeks 1 to 12. The analyses on 75% response in MMDs during Weeks 1 to 4 and Weeks 1 to 12 will be performed as well. Similar response analyses will be performed for MHDs.

For other secondary efficacy endpoints based on response rates, treatment effects of eptinezumab compared to placebo will be analysed using a logistic regression model, similar to the model defined above.

Health-related quality of life scores test between eptinezumab and placebo at Week 4, Week 12, or Week 24 will use the similar ANCOVA model defined in the analysis of key secondary endpoints.

16.8.8 Analysis of the Exploratory Endpoints

The analysis of the exploratory endpoints will be described in the SAP.

16.8.9 Analysis of Subgroups

The analysis specified for the primary and the key secondary endpoints will be repeated for each region (North America and Europe), excluding the region factor, if there are sufficient data collected from the region.

No hypothesis testing will be conducted in the subgroup analysis. Only the treatment differences relative to placebo and their associated 95% CIs will be estimated and displayed using a forest plot.

Other subgroup analyses will be specified in the SAP.

16.9 Safety Analyses

16.9.1 Analysis of Adverse Events

Adverse events will be classified according to the time of onset of the adverse event:

- *pre-treatment adverse event* – an adverse event that starts on or after the date the patient signed the *Informed Consent Form* and prior to the date of first dose of IMP
- *treatment-emergent adverse event* – an adverse event that starts or increases in intensity on or after the date of first dose of IMP

Adverse events, sorted by system organ class and preferred term, will be summarized by treatment group.

Allocation of Treatment-Emergent Adverse Events to Study Periods

Treatment-emergent adverse events may be allocated to study periods (these will be defined in the SAP).

16.9.2 Analysis of Other Safety Endpoints

The vital signs will be summarized by treatment group and period. Potentially clinically significant values will be flagged and summarized.

16.10 Handling of Missing Data

eDiary

Patients who do not complete the eDiary daily will have missing data. It is expected that most missing eDiary data will be sporadic.

For each 28-day period, missing data from the eDiary will be imputed in the following way:

- If the number of days with observations, n, is ≥ 14 days, the MMDs for the 28-day interval will be calculated as the number of migraine days observed/n $\times 28$ (prorated) and rounded off to 2 decimals.
- If n < 14, the MMDs for the period will be set to missing.

Further details on derivation and imputations of days with missing or incomplete eDiary data will be described in the SAP.

Quality of Life Questionnaires

For those questionnaires, missing items will not be imputed. However, strategies will be provided separately in the SAP for calculating sub-score or total score with missing individual scores.

Digital Device Data

No imputation will be taken for missing data in the wearable digital device during the study period.

16.11 Interim Analyses

No interim analysis is planned.

